2.1 Allocated treatment

All patients during the long-term follow-up study are treated with fingolimod 0.5 mg per day. The summaries for data collected during the long-term follow-up study part I will only present one total group (the same as fingolimod any dose). However, patients may have been assigned a different dose (5 mg, 1.25 mg) in their initial fingolimod trial. The summaries for data collected from first dose of fingolimod among all studies will be presented by highest assigned dose of fingolimod; only two groups will be presented: fingolimod 0.5 mg and fingolimod any dose.

2.2 Precision rules

Whenever possible, the minimum and maximum values of the data will be presented to the same precision as the raw data; the mean, median, quartile 1, and quartile 3 will be presented to one more decimal place, and standard deviation will be presented to two more decimal places than the raw data.

2.3 Time frames, baseline, and visit windows

This section defines the study and data time frames, baseline, and rules for visit windows.

2.3.1 Database lock for Study part I

There are two database locks for this study. The analyses specified in this document include data from study part I with a database lock planned around 30th Jun 2017. All qualified patients will have end of study visit scheduled around 31st Oct 2016, which gives time for 6-month follow-up by end of Apr 2017. The 2nd data base lock is planned around 2018 for study part 2, in which patients from the long-term follow-up study are kept for another 2 years after finishing study part I. The analysis plan for study part II will be provided in a separate analysis plan.

2.3.2 Study day

The day of first administration of fingolimod study drug is defined as *Day 1*. Day 1 does not need to occur in the long-term follow-up study.

All other study days will be labeled relative to Day 1. Thus, study day for a particular event date on or after Day 1 is calculated as: (*Date of event – Date of first dose of fingolimod study drug + 1*). An event that occurs prior to Day 1 is calculated as: (*Date of event – Date of first dose of fingolimod study drug*).

In addition to calculating study day with respect to the first dose date of fingolimod drug across all studies, study day will also be calculated relative to the first dose date of fingolimod during the long-term follow-up study.

The number of days after permanent study drug discontinuation will be calculated as (*Date of event – Date of last dose of fingolimod study drug*).

The duration of an event will be calculated as (*Event end date – Event start date + 1*). Day 0 will not be used.

2.3.3 Baseline and post-baseline

Unless otherwise specified, the baseline relative to the first dose of fingolimod (FDF) will be used throughout this study. It is defined as the last available measurement made prior to administration of the first dose of fingolimod among all studies a patient has participated in. The baseline can also be defined relative to the first dose of fingolimod during the long-term follow-up study in certain cases (i.e. ECG summary by visit), which is defined as the last available measurement made prior to administration of the first dose of fingolimod during the long-term follow-up study. The baseline relative to first dose of study drug in the core study (e.g. demographic information, core baseline characteristics) is also used for mentioned sections.

Post-baseline assessments are assessments made after the baseline assessment.

2.3.4 Variables Summarized by Visits

Below are the visit windowing rules used for visits as defined in the Virtual Data Warehouse (VDW) RAP M4 draft version 4.3.

Visit windows will be widely used to align visits across studies. They are based on the assessment schedule of the pivotal studies and comprise a set of days around the nominal visits. The same visit windows will apply to all studies. Visit-windows are non-overlapping; all together they cover the entire study period. Generally, visit-windows are not symmetrical around the nominal visit day. Among all the analysis, ECG, dose monitoring and ‘end of study’ summary for related panels will not use visit-window. Corresponding summaries are based on nominal visits.

Visit windows will be used to present summary statistics by visit. Efficacy data sets consider only scheduled visits, while safety datasets consider both scheduled and unscheduled visits. For efficacy analysis, if multiple assessments are available within a visit window, the record closest to the target day will be selected (if more than one assessment is equidistant to the target day, the later assessment will be used). For safety analysis, multiple assessments within a visit window will be averaged (for quantitative variables) or the worst record (for qualitative variables) will be selected. A follow-up visit-window will be used for data collected after last dose of fingolimod, which only consider scheduled assessments.

Similar rules (record selection either by date closest to target day or by averaging records within the same window) will be applied for efficacy and safety analysis respectively.

Unless otherwise specified, the following vital sign/lab visit windows are derived with respect to the first dose date of fingolimod among all studies.

Table 1 Visit-windows for vital signs and laboratory values

Visit	Start day (time)	Target Day (time)	End day (time)
Week 2**	3	14	22
Month 1	23	30	45
Month 2	46	60	75
Month 3	76	91	136
Month 6	137	182	227
Month 9	228	273	319
Month 12	320	365	410
...		every 3 months	
Month X (row i)	$S_i = \text{Integerpart}((D_i + D_{i-1}) / 2) + 1$	$D_i = \text{Integerpart}(X * 365.25 / 12)$	$E_i = \text{Integerpart}((D_{i+1} + D_i) / 2)$
...	...	Every 3 months	...
Month X (last row)	S_{last}	D_{last}	$E_{\text{last}} = D_{\text{last}} + (D_{\text{last}} - S_{\text{last}})$

- Unless otherwise specified, Day 1 is defined as the first dose day of fingolimod among all studies.
 - Baseline will refer to the last value prior to the intake of the first dose of fingolimod. (Measurements labeled as "pre-dose" assessments will not be used as baseline values if the actual time variable suggests that the value has been obtained after the first dose of study medication: exceptions are body weight and temperature for which Day 1 records can be used as baseline irrespective of the actual time on day 1).
 - Multiple results per patient within a visit window will be averaged for summary statistics by considering both scheduled and unscheduled visits..
 - This visit windowing approach will only be used for summary statistics. (All individual assessments including unscheduled visits will be used to analyze notable and abnormal values, in shift tables and on listings.)
 - ** Week 2 for laboratory values will include day 1 post-baseline as the start day.

Table 2 Visit-windows for efficacy data (non-EDSS) domains

Visit	Start day (time)	Target Day (time)	End day (time)
Month 3	1	91	136
Month 6	137	182	273
Month 12	274	365	547
Month 24	548	730	912
Year 3 (M36)	913	1095	1278
Year 4 (M48)	1279	1461	1643
Year 5 M(60)	1644	1826	2008
Year 6 (M72)	2009	2191	2373
Year 7 (M84)	2374	2556	2739
Year8 (M96)	2740	2922	3104
Year 9	3105	3287	3469
Year 10	3470	3652	3834
Year 11	3835	4017	4200

...		every 12 months	
Month X (row i)	$S_i = \text{Integerpart}((D_i + D_{i-1}) / 2) + 1$	$D_i = \text{Integerpart}(X * 365.25 / 12)$	$E_i = \text{Integerpart}((D_{i+1} + D_i) / 2)$
...	...	Every 12 months	...
Month X (last row)	S_{last}	D_{last}	$E_{\text{last}} = D_{\text{last}} + (D_{\text{last}} - S_{\text{last}})$

- Day 1 is defined as the first dose day of fingolimod among all studies.
 - Baseline will refer to the last MRI value prior to Day 1.
 - For MRI: Visits 777 and 779 (study drug discontinuation assessments: the last scheduled scan is the reference scan), will be included in the visit windowing approach. However, 777 will only be used in a visit window if no other scheduled visit is available in the same window, if another scheduled visit is present, then the scheduled visit will take priority over 777.
 - If multiple assessments are available within a visit window, the record closest to the target day will be selected (if more than one assessment is at the same distance to the target day, the later one will be used for summary statistics (after unscheduled visits are excluded)).

Table 3 Visit-windows for EDSS efficacy data

Visit	Start day (time)	Target Day (time)	End day (time)
Month 3	1	90	135
Month 6	136	180	225
Month 9	226	270	315
Month 12	316	360	405
Month 15	406	450	495
Month 18	496	540	585
Month 21	586	630	675
Month 24	676	720	765
Month 27	766	810	855
Month 30	856	900	945
Month 33	946	990	1035
Month 36	1036	1080	1125
:	:	:	:
Month 72	2116	2160	2205
:	:	every 3 months	:

- Day 1 is defined as the first dose day of fingolimod among all studies.
 - Expanded Disability Status Scale (EDSS) scores will be summarized by visits occurring every 3 months from the date of first dose of study drug (for example at Month 3, Month 6, etc.).
 - Baseline will refer to the last value prior to the intake of the first dose of fingolimod among all studies.
 - If multiple assessments are available within a visit window, the record closest to the target day will be selected (if more than one assessment is at the same distance to the target day, the later one will be used for summary statistics (after unscheduled visits are excluded)).

Table 4 Follow-up visit windows (applicable to several panels: e.g. VSN, LAB, EDSS, MSFC, ██████████)

Visit label	Start day (time)	Target Day (time)	End day (time)
FU (Month 3)	Day 1 p.l.d	Day 90 p.l.d	Day 135 p.l.d
FU (Month 6)	>= Day 136 p.l.d	Day 180 p.l.d	

- Follow-up visit windows are defined relative to study drug discontinuation in the respective pool (unscheduled visits will be excluded).
 - p.l.d = post last dose.

- Day 1 p.l.d is defined as the first day after the *last dose day of fingolimod*.

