- The use of fingolimod in women who are or may become pregnant should only be considered if the potential benefit justifies the potential risk to fetus. Animal studies have shown reproductive toxicity including fetal loss and organ defects, notably persistent truncus arteriosus and ventricular septal defect. Furthermore, the receptor affected by fingolimod (sphingosine-1-phosphate receptor) is known to be involved in vascular formation during embryogenesis. The data available from the use of fingolimod in pregnant women are too limited to draw conclusions on safety of fingolimod in pregnancy. Since it will take approximately 2 months to eliminate the compound from the body upon stopping treatment, risk potential to the fetus may persist and contraception should be pursued during that period. The risk of teratogenic effects of fingolimod is being further addressed in a specific pregnancy registry. Fingolimod is excreted in milk of treated animals during lactation. Because of the potential for serious adverse drug reactions in nursing infants from fingolimod, women receiving fingolimod should not breast feed.
- The safety and tolerability profile did not change over time, as determined in the pooled data of the phase II and III studies and their respective open-label extension studies. In particular, the incidence of malignancies and serious infections did not increase over time. Further long-term data are however needed to better estimate the incidence of rare or time-dependent adverse events.

The current data showed no significant difference on efficacy between the fingolimod 1.25 mg/day and the 0.5 mg/day doses in phase III studies. Fingolimod 0.5 mg/day was associated with an overall more favorable risk/benefit profile than fingolimod 1.25 mg/day. Based on these data, the dose of fingolimod chosen for registration and for further clinical development is 0.5 mg/day.

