## 3 Investigational plan

### 3.1 Study design

This study uses an open-label, multi-center, single treatment arm design allowing patients participating in the fingolimod multiple sclerosis clinical development program to enroll in order to collect additional long-term safety, tolerability, efficacy, and health outcomes data.

This study has two parts:

[figure not shown]
- Part One, collecting long-term safety, tolerability, efficacy, and health outcomes data through approximately 30-Jun-2016, and
- Part Two\*, collecting limited safety data until approximately 30-Jun-2018, in a subset of patients participating in Part One, and other eligible patients from ongoing fingolimod trials (e.g., CFTY720D2312).

\*Eligibility for Part Two is defined as prior fingolimod study patients who are unable to obtain fingolimod outside a clinical trial.

By June 2016, investigators must determine commercial Gilenya eligibility for all active study patients (i.e., reimbursed for commercial Gilenya). Patients able to obtain commercial Gilenya will then have their End of Study (Part One) visit and exit the study, regardless of their post-study treatment decision (i.e., continuing on Gilenya commercially or transitioning to another treatment option). Patients discontinuing or completing the study at Part One who do not continue on commercial Gilenya must return for two follow-up study visits, 3-months and 6-months post-last dose of fingolimod. Patients who choose to continue on commercial Gilenya outside the study are exempted from the follow-up visits.

Patients not eligible for reimbursed, commercial Gilenya will be offered continued study participation in Part Two until their scheduled study visit closest to 30-Jun-2018 (+/- 30 day visit window), with a reduced assessment schedule (see Table 6-2), for the purpose of collecting additional long-term safety and tolerability data in support of the primary study objective. Patients discontinuing or completing the study after entering Part Two who do not continue on commercial Gilenya must return for one follow-up study visit, 3-months post-last dose of fingolimod. Patients who choose to continue on commercial Gilenya outside the study are exempted from the follow-up visit.

Patients enrolling in either part of the study from blinded studies will remain blinded to the identity of the treatment in the previous study. In order to maintain the blind, the monitoring

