### **Guidance on monitoring of patients with notable lymphopenia**

Fingolimod results in sequestration of a proportion of the circulating lymphocytes in lymph nodes with resultant reduction in circulating lymphocyte counts. Average circulating lymphocyte counts are expected to be around  $0.5-0.6 \times 10^9/L$  or  $500-600$  cells/ $\text{mm}^3$ . As such, the absolute total WBC, neutrophil and lymphocyte counts will be measured at each visit  $y$ . If the absolute lymphocyte count drops below  $0.2 \times 10^9/L$  or  $200$  cells/ $\text{mm}^3$  lymphocyte counts should be repeated regularly, at least monthly, and the patient should be reminded of the risk of infections and instructed to promptly report any symptoms of infections to the investigator. If monthly site visits create a logistical burden for the patient, local lymphocyte testing can be performed, with an eCRF comment added that lymphocyte counts were obtained locally and reviewed by the investigator. Study drug should be temporarily interrupted at the discretion of the investigator. Recovery of lymphocyte counts is expected to take approximately 1-2 months after stopping study drug given the long half-life of fingolimod. The patient should be evaluated and monitored for infections on a regular basis during this period.

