2.5 Analysis sets

The following analysis sets will be defined.

- **Enrolled set:** The enrolled set will include all patients who entered the long-term follow-up study part I (excludes long-term follow-up study screen failures), but will exclude patients with protocol deviation severity code of 8 (8=exclude from all analyses) in the long-term follow-up study part I.
- **Safety set:** The safety set will include all patients who entered the long-term follow-up study part I and received at least one dose of fingolimod in any study, but will exclude patients with protocol deviation severity codes of 5 (5=exclude from all safety analyses) and 8 (8=exclude from all analyses) in the long-term follow-up study part I. Note that all data reported in the long-term follow-up study part I will be analyzed, including assessments or events which started before the long-term follow-up study part I.
- **Fingolimod safety set:** The fingolimod safety set will include all patients who entered the long-term follow-up study part I and received at least one dose of fingolimod in any study, but will exclude patients with protocol deviation severity codes of 5 (5=exclude from all safety analyses) and 8 (8=exclude from all analyses) during the core study prior to entry to the long-term follow-up study part I. For patients with such protocol deviations after the core study, record level data associated with the protocol deviations will be excluded from the analysis.

- **Fingolimod full analysis set:** The fingolimod full analysis set will include all patients who entered the long-term follow-up study part I and received at least one dose of fingolimod in any study but will exclude patients with protocol deviation severity codes of 0 (0=exclude from all efficacy analyses) and 8 (8=exclude from all analyses) during the core study prior to entry to the long-term follow-up study part I. For patients with such protocol deviations after the core study, record level data associated with the protocol deviations will be excluded from the analysis.
- **Follow-up set:** The follow-up set will consist of all patients in the safety set who have any follow-up visit data or at least one safety record after the study drug discontinuation. It will be used for summary of adverse events and concomitant medications with occurrences after last dose of fingolimod only.

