8.3.3 Analysis of 6-month confirmed disability progression

Disability progression in this study is defined based on an increase in the EDSS score by 1.5 point for patients with a FDF baseline EDSS score of 0, 1 point for patients with FDF baseline EDSS of ≥ 1 and ≤ 5.5 , and by 0.5 points for patients with an FDF baseline EDSS > 5.5 , confirmed after 6 months and all intermediate EDSS assessments. A 6-month confirmed disability progression is defined as a 6-month sustained increase from the reference (potential onset of progression) value in the EDSS scores. i.e., every EDSS score (scheduled or unscheduled) within a 6-month duration after the first progression should

meet the progression criteria as specified above. The confirmation can only happen at a scheduled visit.

To evaluate disability progression, all available scheduled and unscheduled EDSS assessments after the reference time point (e.g. Day 1) will be compared to the EDSS at the reference time point to assess if the change from the reference time point meets the disability progression criteria. The disability progression onset date will be the date of the first EDSS score meeting the disability progression criteria.

The disability progression confirmation can only happen at a scheduled visit and in the absence of a relapse. Note that the end of study or early discontinuation visit and the follow-up visit are protocol specified visits and will be treated as scheduled visits and thus can be used to confirm a disability progression if applicable. Specifically, the confirmation visit for 6-month confirmed disability progression will be the first scheduled visit meeting the following conditions:

- The confirmation visit needs to be ≥ 166 days from the potential onset date and the disability progression criterion needs to be met at that visit (and all visits in between the onset and the confirmation).
- The EDSS is not performed during a relapse (information collected as a flag in the CRF).
- All available EDSS scores (scheduled or unscheduled) between the disability progression onset and this visit meet the disability progression criteria.

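### The Part I FU (Month 3) window opens the day after the last dose, so completion-visit values, including those of patients still on fingolimod, can enter the follow-up means

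*SAP*

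**What the plan says.** All SAP references are to the Part I SAP unless stated.

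- **Window.** Section 2.3.4: "A follow-up visit-window will be used for data collected after last dose of fingolimod, which only consider scheduled assessments". Table 4 covers vital signs, laboratory, EDSS and MSFC among others. FU (Month 3) is Day 1 to Day 135 after the last dose (target Day 90); FU (Month 6) starts on Day 136 (target Day 180). The table note gives the anchor: "Follow-up visit windows are defined relative to study drug discontinuation in the respective pool". Only unscheduled visits are removed.
- **Several records in one window.** The sentence after the follow-up rule refers to "record selection either by date closest to target day or by averaging records within the same window", the first for efficacy and the second for safety.
- **The completion visit.** Protocol Table 6-1 collects hematology, chemistry and vital signs at Study Completion or Premature Discontinuation and dispenses no drug there. SAP 8.3.3 says that this visit and the follow-up visit "are protocol specified visits and will be treated as scheduled visits". That rule is written for EDSS; the SAP gives no different rule for laboratory data.
- **Who has follow-up visits.** Protocol 3.1: "Patients who choose to continue on commercial Gilenya outside the study are exempted from the follow-up visits". Table 6-1, footnote 14, limits follow-up visits to patients who do not go on with fingolimod in any setting.
- **Follow-up set.** Section 2.5 defines it as "all patients in the safety set who have any follow-up visit data or at least one safety record after the study drug discontinuation". It is the basis for the tables of adverse events (9.1.2.1) and medications (7.3) after the last dose.
- **Pharmacology.** Protocol 1.1: "it will take approximately 2 months to eliminate the compound from the body upon stopping treatment". Protocol Appendix 5: "Recovery of lymphocyte counts is expected to take approximately 1-2 months after stopping study drug given the long half-life of fingolimod".

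**The concern.** A laboratory value taken a few days after the last capsule still reflects treatment by the protocol's own account. Table 4 nevertheless puts it in the same column as a value taken three months later, and the averaging rule blends the two. A patient who switches to commercial drug can contribute a value to FU (Month 3) without having stopped fingolimod.

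Safety is the primary objective. Protocol Section 9 describes the follow-up data as coming after discontinuation of study treatment, and SAP 9.1.2.1 states that its post-last-dose table is meant to show which events follow the stopping of fingolimod. If treated and untreated observations are mixed, neither the follow-up means nor those tables can be read that way.

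**Working it through.** 1. **Table 4 reproduced.** With targets 90 and 180, the end of FU (Month 3) is int((90 + 180)/2) = 135 and the next window starts at 136, as stated. The Day 1 start copies the first rows of Tables 2 and 3. Table 1's midpoint rule, S = int((D_i + D_(i-1))/2) + 1 with the last dose as 0, would give int((0 + 90)/2) + 1 = 46.

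2. **Against the protocol visit.** FU1 is due 3 months ± 14 days after the last dose (Table 6-1, footnote 14), and a month is 30 days (Section 6), so Day 76 to Day 104. Days 1 to 75 come before the earliest in-tolerance FU1: 75/135 = 56% of the window.

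3. **Which completion records enter.** Days after discontinuation are the event date minus the last-dose date (SAP 2.3.2). A completion visit on the last-dose day is Day 0 and stays out. One day later it is Day 1 and goes in.

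4. **Overlap with the 45-day rule.** SAP Section 9 keeps assessments up to 45 days after the last dose in the ordinary post-baseline safety summaries. A completion record on Days 1 to 45 therefore qualifies both for those summaries and for FU (Month 3). The midpoint start of Day 46 would remove this overlap.

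5. **One patient with both records.** Let L be the on-drug lymphocyte level and R the level at FU1. The average shows ((L + R)/2 - L)/(R - L) = 1/2 of the true change, whatever R is. Take L = 0.55 (middle of the 0.5-0.6 × 10^9/L in Appendix 5) and assume R = 1.2, 1.5 or 1.8, which the documents do not give. The reported values are 0.875, 1.025 and 1.175.

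6. **Group mean.** Let a, b and c be the shares of contributors with FU1 only, both records, and a completion record only (a + b + c = 1). The mean is aR + b(L + R)/2 + cL, so the fraction of the change shown is a + b/2. All shares below are assumptions.

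| a | b | c | Mean at R = 1.2 / 1.5 / 1.8 | Change shown |
|---|---|---|---|---|
| 1 | 0 | 0 | 1.2 / 1.5 / 1.8 | 100% |
| 0.5 | 0.5 | 0 | 1.0375 / 1.2625 / 1.4875 | 75% |
| 0.5 | 0 | 0.5 | 0.875 / 1.025 / 1.175 | 50% |
| 0 | 0.5 | 0.5 | 0.7125 / 0.7875 / 0.8625 | 25% |
| 0 | 0.1 | 0.9 | 0.5825 / 0.5975 / 0.6125 | 5% |

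7. **Outputs outside the problem.** EDSS and MSFC take the record closest to Day 90, so a completion record counts only when there is no FU1 record. The notes to Table 1 restrict windowing to summary statistics, so notable-value, shift and listing outputs are unaffected. The Part 2 SAP (2.3.4) summarizes safety by nominal visit, so the window problem is confined to Part I.

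8. **Follow-up set.** One safety record after the last study dose is enough for entry. A commercial patient qualifies through a completion visit on Day 1 or later. Such a patient also qualifies through a serious event in the 6 weeks after stopping participation, which Protocol 7.2 requires sites to report. Neither route requires the patient to have stopped fingolimod.

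**The case against.** The best defence is that the plan does not intend this.

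- Section 2.3.4 says end-of-study summaries use nominal visits, Section 9 speaks of summaries of the Month 3 and Month 6 follow-up visits, and Section 3 counts the patients expected at and returning for those visits. An inflated follow-up column could be noticed against that count. This makes exclusion a plausible intention. But the end-of-study summary is a separate output, and no sentence withholds the record from Table 4.
- The windows come from a data-warehouse document that is not available here, and the scheduled-visit rule in 8.3.3 concerns EDSS. Both are fair reasons for caution. However, where the SAP wants special handling it says so: under Table 2, MRI discontinuation visit 777 gives way to another scheduled visit in the same window. Laboratory data and vital signs have no such rule.
- For completers the gap may be short. Up to 6 × 35 = 210 capsules are supplied, which covers 180 days plus the 30-day visit tolerance, and unused drug is collected at completion. This stands, and it means the bias may be small or absent. A last capsule taken the day before still gives Day 1, though, and early discontinuers may have longer gaps.

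A reader might infer that on-drug values are in fact being reported as off-drug recovery, or that lymphocyte reversibility is understated by some definite amount. The documents support neither. Entry to the window depends on visit dates that they do not give. Table 4 labels the column FU (Month 3), the SAP overview gives continued safety monitoring as the purpose of these visits, and no objective concerns reversibility. A recovery time after stopping is stated for lymphocytes only, not for liver tests or blood pressure.

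**Conclusion.** The point holds in conditional form. Followed as written, the Part I SAP can place completion or discontinuation records in FU (Month 3), can average them with true FU1 values in laboratory and vital-sign means, and can let patients still on fingolimod into both the follow-up columns and the follow-up set.

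The size cannot be determined. The half-change result for a patient with both records needs only the premise that the first is still at the on-drug level. Every group figure rests on assumed shares and an assumed recovered value, and runs from no bias (no completion record after the last-dose day) to nearly all of the change hidden. The study is descriptive, so no test or error rate is involved. The fault should still be corrected, because it concerns the post-treatment part of the primary safety objective and costs little to put right.

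**What to change.** In the Part I SAP:

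- Base the follow-up summaries on the nominal FU1 and FU2 visits, in line with the Part 2 SAP's use of nominal visits for safety.
- State that Study Completion and Premature Discontinuation records do not enter the FU windows.
- Exclude patients recorded as continuing fingolimod, commercially or in Part Two, from the FU summaries and from the follow-up set.

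The cost is a few sentences, a change to the window derivation and smaller numbers in the FU columns. No new data should be needed, since Section 3 already requires the patients expected to have follow-up visits to be identified. Opening the window only after the 2-month elimination time, or splitting the post-last-dose adverse event table at Day 60, would be optional refinements and is not needed to correct the fault.
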